Factors influencing catheter migration include weight, body mass index, depth of the epidural space and patient positioning (9,10). Bishton et al documented inward migration in 13% and outward displacement of one or more centimeters in 22% of patients in a cohort of 153 laboring patients (10). They also found that all cases of failed epidural occurred in patients with outward migration greater than 2,5 cm (10). Hamilton et al showed an association between patient position change and movement of epidural catheters, when the patient is sitting with a straight back and when placed on lateral decubitus position (11). The authors found that the magnitude of epidural catheter movement was more pronounced in patients with $BMI > 30 \text{ kg/m}^2$. It has been hypothesized that the epidural catheter might be fixed to the ligamentum flavum after it is threaded, as the maximum pressure found during catheter placement corresponds to this anatomical structure (12). When the patient changes position after taping the catheter, especially in the case of a parturient with high BMI, the new anchor point theoretically moves to the skin, facilitating outward migration of the epidural catheter (9).

Some authors have evaluated the influence of different dressing methods on epidural catheter migration. Burns et al compared Tegaderm™ dressing, Tegaderm™ plus filter-shoulder fixation and Niko Epi-Fix dressing in 113 patients in labor (2), finding that Tegaderm™ plus filter-shoulder was superior in terms of minimization of epidural catheter displacement. Their study doesn't mention weight or BMI of patients included in the study. Odor et al evaluated the efficacy of Epi-Fix™, Lockit Plus® and Tegaderm™ for dressing of intrapartum catheters, finding superiority of the Lockit Plus® system to decrease catheter migration and epidural analgesic failure (13). The authors didn't evaluate the effect of BMI on the outcomes and even excluded patients with $BMI > 50 \text{ kg/m}^2$. Similar results were reported by Clark et al in a cohort of 102 patients having epidural catheters for major non-obstetric procedures (14).

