- a. *Procedures involved to include those procedures that are standard evaluation and/or care and those that are solely for research purposes:*

After approval by the Institutional Review Board, we will obtain consent from the participant patients. Patients will be randomized using a random number table to be allocated to one of three groups with sealed envelopes, based on the type of dressing to be used to secure the epidural catheter after its insertion:

- 1) Tegaderm™ plus SorbaView SHIELD® dressing
- 2) Dressing with Tegaderm™ plus Steri-Strip™ bands in addition to a catheter support pad (All included in the epidural kit)
- 3) dressing with Tegaderm™ only

Patients will have an epidural catheter placed for labor. We will use the standard epidural kit (Smiths Medical ASD Inc. Keene, NH. USA). The technique will consist of the use of a 17G Tuohy needle using a midline

approach with the patient in the sitting position. Localization of the epidural space will take place using loss of resistance to air or saline per anesthesiologist's preference. A 20G epidural catheter will be inserted to leave 5 cm into the epidural space (distal to the tip of the Tuohy needle). After the Tuohy needle is removed and the catheter is considered to be at an adequate depth, the patients will be asked to sit up straight. Then, a test dose with 3 mL of Lidocaine 1,5% with epinephrine 1:200.000 will be injected through the catheter into the epidural space, and a dressing varying depending on the assigned group will be applied. The rest of the catheter will be secured longitudinally along the patient's back over the shoulder.

b. Study design:

This is a randomized controlled clinical trial.

c. Procedures performed to lessen the probability or magnitude of risks:

The application of the three types of epidural dressings analyzed in this study are part of our current standard clinical practice. There is no additional risk due to our intervention. We will protect the rights of the patient maintaining confidentiality (records will be de-identified and assigned a study number) and patients can revoke their consent to participate at any moment during the study. Visual evaluation of the site of insertion of the epidural catheter will be inspected during the study period and any signs of topical or allergic reactions to any of the components used for dressing will be identified and treated accordingly should it happen.

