d. Duration of an individual subject's participation in the study and the time involved:

The patients will be participating in the study for as long as the epidural catheter remains in place for clinical indications. The expected time will be between 6 and 12 hours.

7. Data and Specimen Management

a. Data analysis plan:

Sample size: Based on previous experiences for a measurable difference of 0,5 cm, we will include 35 patients in each group to have a power of 90% and a statistical significance level of 0,05. Data will be analyzed using analysis of variance, Student's t test, chi-square test and Pearson's correlation coefficients where appropriate.

N/A

b. Power analysis:

See above

N/A

c. Data handling:

N/A

i. Information included in the data

Following dressing application, demographic variables of each patient will be recorded including (age, gravity, parity, weeks of gestation, weight, height, BMI). Other recorded variables include time of insertion, distance from catheter tip to skin in centimeters. One hour after delivery, immediately before catheter removal, time, duration of catheter presence, centimeters from skin to catheter tip and dressing integrity will be recorded. Dermatomal level and symmetry of the block will be recorded every two hours or every time the patients requires a top-up dose. We will also record number of top up doses and rate of epidural infusion as well as the need for catheter replacement during the observation period.

Primary outcomes

Epidural catheter migration (ECM) in centimeters = Distance from tip to skin at insertion - Distance from tip to skin at removal. If the catheter moves inward, ECM will be negative and if it gets displaced outwardly, ECM will be positive.

Secondary outcomes

- 1) Dermatomal sensory level measured with thermal discrimination
- 2) Incidence of asymmetric block
- 3) Rate of epidural catheter replacement
- 4) Total epidural dose (mL)
- 5) Number of top-up epidural boluses.

ii. Data storage

Data derived from the study will be stored in a locked drawer in the office of the PI for the duration of the study. The de-identified information will be accessed by the research team and the statistician for analysis.

iii. Duration of data storage

For one year after study completion.

iv. Access to data

The PI and the research team.

v. Responsible for receipt or transmission of the data

The Principal Investigator

vi. Data transport

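### The primary outcome is a change score compared without adjustment for its own baseline, although that baseline is recorded and tracks a factor the protocol says influences migration: a modest loss of precision, not a bias

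*Combined protocol and SAP*

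**What the plan says.** - **Outcome.** Section 7.c.i, Primary outcomes: "Epidural catheter migration (ECM) in centimeters = Distance from tip to skin at insertion - Distance from tip to skin at removal". Outward movement is positive and inward movement negative.
- **Analysis.** Section 7.a lists "analysis of variance, Student's t test, chi-square test and Pearson's correlation coefficients where appropriate". No test is assigned to ECM, and no regression, analysis of covariance or baseline term appears anywhere.
- **Baseline reading.** Section 7.c.i records "time of insertion, distance from catheter tip to skin in centimeters". The paragraph opens by placing data recording after the dressing has been applied.
- **Link to depth.** Section 6.a: "A 20G epidural catheter will be inserted to leave 5 cm into the epidural space". Baseline tip-to-skin distance is therefore roughly skin-to-space depth plus 5 cm.
- **Depth as a factor.** Section 2: "Factors influencing catheter migration include weight, body mass index, depth of the epidural space and patient positioning". The secondary aims in section 1 cover BMI, indwelling time, insertion level and height, but not depth.
- **Allocation.** Section 6.a describes a random number table and sealed envelopes, with no stratification.
- **Sample size.** Sections 4 and 7.a: "we will include 35 patients in each group to have a power of 90% and a statistical significance level of 0,05". The target is a 0.5 cm difference, justified only by unspecified earlier experience. No SD is given.

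**The concern.** The protocol names a likely prognostic factor and collects a close proxy for it. It uses that proxy only as one half of a subtraction. Subtracting the baseline is not the same as adjusting for it: if the amount of movement depends on depth, ECM remains correlated with the baseline distance.

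Two things follow. The part of ECM explained by depth stays in the error term and widens the confidence intervals. Also, a chance difference in depth between arms passes into the dressing contrast, and the unstratified allocation does nothing to limit it. The listed Pearson correlation could describe how baseline relates to ECM, but it does not adjust the comparison of dressings.

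Prespecification matters here because the research team both collects and analyses the data (section 8.e) and reviews the cumulative data weekly (section 8.f). If the covariate is not named in advance, the decision to adjust could be taken after an imbalance has been seen.

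**Working it through.** **Inputs from the documents:** 35 per arm, difference 0.5 cm, power 90%, alpha 0.05. **Assumed:** a two-sided pairwise t test with 68 degrees of freedom; the SD of ECM; and r, the within-arm correlation of baseline distance with ECM.

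**1. The plan's own figure.** The 35 per arm cannot be reproduced forwards, because no SD is stated. Solving backwards by the normal approximation:

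SD = 0.5 / [√(2/35) × (1.960 + 1.282)] = 0.5 / (0.2390 × 3.242) = 0.645 cm.

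The noncentral t gives 0.636 cm, which is used below. An SD of 1.0 cm is added as an assumed less favourable case.

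**2. Precision.** With the baseline in the model, residual SD = SD × √(1 − r²), and effective n per arm = 35 / (1 − r²).

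| r (assumed) | Variance removed | Effective n per arm | Power, SD 0.636 | Power, SD 1.0 |
|---|---|---|---|---|
| 0 | 0% | 35.0 | 90.0% | 54.1% |
| 0.2 | 4% | 36.5 | 91.1% | 55.8% |
| 0.3 | 9% | 38.5 | 92.5% | 58.0% |
| 0.4 | 16% | 41.7 | 94.3% | 61.4% |

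A simulated three-arm trial with 35 per arm, fitted with and without the covariate, gave variance ratios for the contrast of 0.96 at r = 0.2 and 0.91 at r = 0.3. At r = 0 adjustment cost 0.3 to 0.5 percentage points of power.

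**3. Chance imbalance.** The difference in mean baseline between two arms has standard error √(2/35) = 0.239 baseline SDs. The probability that a given pair differs by more than 0.25 SD is 2 × [1 − Φ(0.25/0.239)] = 0.30. For at least one of the three pairs it is 0.55 by simulation. The resulting shift in the unadjusted contrast is r × 0.25 × SD. At r = 0.3 and SD 0.636 this is 0.3 × 0.25 × 0.636 = 0.048 cm, about 10% of the 0.5 cm target.

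**4. If BMI is also in the model.** Assume BMI correlates 0.3 with ECM (R² = 0.09 alone) and c = 0.4 to 0.6 with depth. Then

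R² = (0.3² + r² − 2 × 0.3 × r × c) / (1 − c²).

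| r | R², c = 0.4 | R², c = 0.6 | Points added to 0.09 |
|---|---|---|---|
| 0.2 | 0.098 | 0.091 | 0.8 to 0.06 |
| 0.3 | 0.129 | 0.113 | 3.9 to 2.3 |
| 0.4 | 0.183 | 0.166 | 9.3 to 7.6 |

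Beyond BMI, the baseline therefore adds about 0.1 to 9 points of R² over this range, and almost nothing at r = 0.2.

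**The case against.** - **Validity.** Under randomisation the unadjusted comparison of ECM is unbiased, and its standard error already allows for chance imbalance. This stands. A reader might infer that the planned analysis gives a biased dressing effect; the documents do not support that.
- **r has no source in the documents.** Section 2 gives neither size nor direction for the effect of depth. ECM is signed, and the Background reports both inward and outward migration. If depth increases movement in either direction, it widens the spread of ECM without shifting its mean, and the linear correlation could be near zero. This stands, and is why r = 0 is in the table.
- **The proxy is imperfect.** The 5 cm is a nominal target. Section 6.a has the woman sit up straight after the needle is removed and before dressing, and section 2 reports that position change moves catheters. Adjustment removes only the linear part carried by this proxy, not all depth-related variation.
- **Timing.** Section 7.c.i can be read as placing the baseline reading after the randomised dressing is on, so it may not be a clean pre-treatment covariate. This stands and has to be settled in the same revision.
- **Other readings of the analysis section.** No test is tied to ECM, so an unadjusted ANOVA or t test is inferred from the list. The inference is fair, because nothing else listed compares a continuous outcome across arms. It would be wrong, however, to say that the baseline is unused: it is half of ECM.
- **A larger problem lies elsewhere.** At SD 1.0 cm, adjustment at r = 0.4 reaches only 61% power. The missing SD is a separate and bigger defect, which adjustment does not cure.

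**Conclusion.** The point holds as one of efficiency. The plan leaves an already recorded and plausibly prognostic baseline out of the primary comparison, at some cost in precision and in protection against chance imbalance.

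The size depends wholly on an assumed r. The gain in power is about 1 to 2 points at r = 0.2, 2 to 4 at 0.3 and 4 to 7 at 0.4, across the two SDs. At r = 0 there is a loss of at most about half a point. A reader might infer that baseline depth is sure to add materially once BMI is in the model. That does not hold across the assumed range, since at r = 0.2 it adds less than one point of R².

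The change is worth making because it costs almost nothing and settles the choice of covariate before any data are seen. The current plan is not invalid without it.

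**What to change.** In section 7.a:

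1. Prespecify the ECM comparison as a linear model with dressing arm and baseline tip-to-skin distance (cm, continuous).
2. Report adjusted pairwise differences between dressings with confidence intervals, and show the unadjusted result as a check.
3. State that the covariate is the same at-insertion reading that enters ECM and that it is taken before the assigned dressing is applied. Align the recording paragraph in section 7.c.i with this.

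The cost is a change of wording and one degree of freedom. No new variable is needed; the only practical point is to fix the moment of the baseline reading.

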COVER PAGE

Official Title of the Study

Intrapartum epidural catheter displacement: Comparison of three dressing methods in morbidly obese parturients

NCT Number

NCT03574441

Protocol Title: *Intrapartum epidural catheter displacement: Comparison of three dressing methods in morbidly obese parturients*

Principal Investigator: *[name] MD*

1. Objectives

Purpose, specific aims, and hypothesis:

Purpose: We propose this study to prospectively evaluate the efficacy of the three types of epidural catheter dressings that we currently use in our Labor and Delivery unit, in terms of catheter migration, taking into consideration the influence of body mass index on this variable.

Primary aim: We will evaluate the efficacy of three different epidural catheter dressing systems in laboring patients.

Secondary aims: To compare the effect of different degrees of obesity measured by BMI, on epidural catheter migration and quality and failure of epidural labor analgesia. To evaluate the effect of time an indwelling catheter remains in place, level of insertion and patient's height on epidural catheter migration.

Hypothesis: The use of dressing with transparent TegadermTM plus SorbaView SHIELD® dressing is superior to the dressing with TegadermTM plus Steri-StripTM bands in addition to a catheter support pad, and to a dressing with TegadermTM only, for epidural catheter fixation in laboring obese and morbidly obese patients, in terms of catheter migration, epidural quality and failure and epidural catheter replacement in the labor analgesia setting.

2. Background

Background and rationale for the study:

Failure of labor epidural is a well-recognized situation in obstetric anesthesia practice. Incidence of epidural failure was shown to be 12% in a retrospective analysis of 19.259 deliveries (1). Epidural migration has been documented in both the obstetric and non-obstetric settings (2,3). It has been argued that prevention of epidural displacement is a potential remedy to at least part of the incomplete or failed epidurals in obstetrics (4,5). Motamed et al showed that 45% of epidural failures in major abdominal surgery could be attributable to catheter migration (6). Phillips et al studied epidural catheter migration in labor finding an incidence of 54% (7). Migration was 2 cm on average and tended to be directed inward. Crosby et al found a similar incidence of catheter migration but in an outward direction (8).

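### The removal reading of catheter position has a fixed time but no fixed or recorded posture, so posture variation can enter the primary outcome and cannot be told apart from lasting migration

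*Combined protocol and SAP*

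**What the plan says.** Section 6.a describes the steps at insertion. Once the needle is out and the catheter depth is accepted, "the patients will be asked to sit up straight"; the test dose and the allocated dressing come next. Section 7.c.i places the first reading after the dressing: "Other recorded variables include time of insertion, distance from catheter tip to skin in centimeters". The posture for that reading is implied by the order of steps and is not stated.

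The second reading is described in the same section: "One hour after delivery, immediately before catheter removal, time, duration of catheter presence, centimeters from skin to catheter tip". That fixes the time. No posture is given, and posture is not among the recorded variables.

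The primary outcome is the plain difference, "Distance from tip to skin at insertion - Distance from tip to skin at removal", with outward movement positive. Section 7.a lists analysis of variance, t test, chi-square test and Pearson correlation, with no adjustment for posture.

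Section 2 reports "an association between patient position change and movement of epidural catheters", naming sitting with a straight back and lateral decubitus, and adds that "the magnitude of epidural catheter movement was more pronounced in patients with" a BMI above 30 kg/m². Section 3 enrols only patients above that value. Section 1 includes a secondary aim: "To compare the effect of different degrees of obesity measured by BMI, on epidural catheter migration".

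**The concern.** A difference of two readings measures migration cleanly only if both are taken under the same conditions. Here the plan's own background names a condition that matters, posture, and says it matters more in the kind of patient enrolled. The procedure settles the posture at dressing and leaves it open at removal.

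Two things are at stake. For the primary outcome, removal postures that vary between patients widen the spread of ECM and cost power against a target difference of 0.5 cm. For the secondary BMI aim, randomisation gives no protection: if the posture shift rises with BMI within the enrolled range, part of any correlation between BMI and ECM would come from how patients were positioned when read. Since posture is not recorded, neither effect could be examined afterwards.

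**Working it through.** **Inputs from the documents.** Target difference 0.5 cm, 35 per group, three groups (105 in total), power 90%, significance level 0.05 (sections 4 and 7.a). Neither an SD nor the size of a posture shift in centimetres is given, so the results below are illustrations.

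**Step 1, the planned sample size.** Without an SD, 35 per group cannot be reproduced; the SD it implies can be solved for. For a two-sided two-sample t test with 68 degrees of freedom, the noncentrality is 0.5 / (SD × √(2/35)), and √(2/35) = 0.239. Power is 90% when SD = 0.636 cm (variance 0.405). Other readings of the calculation (normal approximation, one-sided, Bonferroni over three pairs, three-group F test) give about 0.56 to 0.71 cm.

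**Step 2, noise in the dressing comparison.** Assume a proportion p of removal readings is taken in a posture that shifts the reading by d, unrelated to arm. The added variance is p(1 − p)d², which is 0.25d² at p = 0.5, its largest value.

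| d (cm) | Total variance | Total SD (cm) | Noncentrality | Power, 35 per group |
|---|---|---|---|---|
| 0 | 0.405 | 0.636 | 3.29 | 90% |
| 0.5 | 0.405 + 0.0625 = 0.467 | 0.683 | 3.06 | 85% |
| 1.0 | 0.405 + 0.25 = 0.655 | 0.809 | 2.59 | 72% |
| 1.5 | 0.405 + 0.5625 = 0.967 | 0.983 | 2.13 | 55% |

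The expected difference between arms is unchanged throughout, so this is lost precision and not bias.

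**Step 3, the BMI correlation, same posture scenario.** Assume no true BMI effect, half of removal readings shifted, a shift growing by g = 0.02 to 0.03 cm per BMI unit, and a BMI SD of 6 to 8. All of these are assumptions. Approximately, r = 0.5 × g × SD of BMI / √((0.5 × g × SD of BMI)² + 0.636²).

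- Low end: 0.5 × 0.02 × 6 = 0.06, and 0.06 / √(0.0036 + 0.405) = 0.09.
- High end: 0.5 × 0.03 × 8 = 0.12, and 0.12 / √(0.0144 + 0.405) = 0.185. Simulation, which also counts the extra variance from mixed postures, gives about 0.18.

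With 105 patients, Fisher's z has standard error 1/√102 = 0.099. For r = 0.09, z / SE is about 0.91 and a two-sided 5% test rejects about 15% of the time. For r = 0.18, z / SE is about 1.84 and it rejects about 45% of the time. Simulation agrees. If the shift is flat above BMI 30 (g = 0), r is zero and the rate stays at 5%.

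**Step 4, reading resolution (a minor, separate point).** The distance is recorded "distance from catheter tip to skin in centimeters" with no precision set. Rounding both readings to width w adds 2w²/12 to the variance. For w = 1 cm: 0.405 + 0.167 = 0.571, SD 0.756, power 78%. For w = 0.5 cm: 0.405 + 0.042 = 0.446, SD 0.668, power 87%.

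**The case against.** Several counter-arguments have force.

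- **The movement may be real.** Section 2 also suggests that position change after taping moves the anchor point to the skin and favours outward migration. Both readings come after dressing, so part of a posture-related shift may be the outcome that the dressings are meant to prevent. This stands. It is also a reason to fix the posture: without a common one, a temporary shift at the time of reading and lasting migration cannot be separated.
- **The planning SD may already include posture variation.** The sample size rests on unspecified previous experience. If that included ordinary variation in posture and reading precision, adding it again counts it twice and the loss is nil. The documents cannot settle this.
- **The team is small.** The investigator and two co-investigators, who helped write the protocol, collect the data (sections 8.e and 15.b). That limits inconsistent practice without excluding it, and silence on posture does not show that practice varies.

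A reader might infer more than the documents support. One inference is that the dressing comparison is biased: allocation is randomised, and nothing suggests that removal posture differs by arm. Another is that the BMI analysis is biased as a matter of fact: section 2 reports only more movement above BMI 30, every enrolled patient is above 30, and continued growth within that range is not shown. A third is to assume that every removal reading is out of posture, which raises r to 0.19–0.35 and significance to 47–96% of trials. That cannot be set beside the power losses in the table, which need a mixture of postures: a common shift in all patients adds no variance to the arm comparison.

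**Conclusion.** The gap is real and the protocol's own background supplies the mechanism: varying posture at removal can add noise to the primary outcome that the recorded data cannot remove. How much is unknown. Under the scenario worked above, the cost ranges from no power loss to a fall from 90% to 55%. Bias in the BMI–migration analysis is a possibility, conditional on the shift still growing above BMI 30; with half of readings affected and the assumed slopes, the false-positive rate would be about 15–45% instead of 5%. The trial remains viable. This is a cheap improvement to a measurement definition and not a flaw that invalidates the dressing comparison.

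**What to change.** In section 7.c.i, state that both tip-to-skin readings are taken with the patient in the same upright sitting posture as at dressing. Add a field for the posture actually used when that is not possible, and specify a sensitivity analysis of ECM, including the BMI analysis, that excludes those readings. Separately, record both readings to 0.5 cm or finer, given the 0.5 cm target difference.

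The cost is a sentence or two of protocol text, one field on the form, and a few flagged patients who cannot sit up one hour after delivery. No extra patients, visits or staff are needed. The change has to be made prospectively, because a posture that was not recorded cannot be recovered later.

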From the site of data collection to the PI office by the Principal Investigator.

8. Provisions to Monitor the Data to Ensure the Safety of Subjects

a. Data safety and delivery plan

The Principal Investigator (PI) will be responsible for the conduct of this study, including overseeing participant confidentiality, executing the Data and safety Monitoring (DSM) plan, and complying with all reporting requirements to local and federal authorities. This oversight will be accomplished through additional oversight from a Data and Safety Monitoring Committee at the Augusta University. We will conduct ongoing review of all serious adverse events (SAEs), unanticipated problems (UAPs) and reportable adverse events (AEs). Per the DSM Plan, SAEs, UAPs and reportable AEs will be reported to the institutional committee and IRB per study protocol. All SAEs, UAPs and reportable AEs are to be reported to the committee and IRB within 5 business days of receiving notification of the occurrence.

Audits will consist of a review of the regulatory documents, consent forms, and source data verification. Results and recommendations from audits will then need to be submitted by the PI to the IRB of record at the time of the continuing review.

b. Data review.

We will review the results for analysis at the end of data collection. The participants will be informed from the beginning of the study that any concerns related to the study be communicated directly to the PI, who will address them according to the DSM plan.

c. Collection of safety information

Data will be de-identified right after collection and be kept as paper record in the PI office.

d. Frequency of data collection

Data will be collected daily.

e. Responsible of data review.

The research team (PI and 2 co-investigators) will collect and analyze data.

f. Frequency of data review

Every week there will be a review of the cumulative data.

g. Conditions that trigger an immediate suspension of the research.

N/A

9. Withdrawal of Subjects

N/A

a. Anticipated circumstances under which subjects will be withdrawn from the research without their consent.

Patients will be withdrawn from the study if she develops an allergic or topical reaction to dressing or if the dressing has to be replaced due to soiling or bleeding.

N/A

b. Procedures for orderly termination.

N/A

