If during the preliminary data review one of the dressings is performing significantly better or worse than the others, or if one of the groups has higher incidence of catheter migration than that reported in the literature, the study will be terminated and the results analyzed up to that point.

c. Procedures that will be followed when subjects withdraw from the research

N/A

If there is withdrawal of consent or if a subject is withdrawn without consent for the circumstances cited above, those cases will be included in the analysis as "lost to follow-up" and reported in the results section.

10. Risks to Subjects

a. *Foreseeable risks.*

No risks additional to standard clinical care are foreseen. Topical or allergic reactions to the dressing materials would be managed by removal of the dressing and topical treatments.

b. *Costs that subjects may be responsible for because of participation in the research.*

N/A

N/A

c. *Risks to others who are not subjects.*

N/A

N/A

11. Potential Benefits to Subjects

There is no direct benefit to patients expected from their participation in this study. It is hoped the knowledge gained will be of benefit to other patients in the future.

12. Confidentiality

Procedures for maintenance of confidentiality.

See above

13. Consent Process

Before enrollment in the study, patients will be explained the purposes of the study, the risks and the procedures that will take place as part of the study. Time will be given to answer questions and PI contact information will be provided. Then, the patient will be given the opportunity to decide about participation in the study by signing the consent. The possibility of revoking the consent at any time during the study will also be explained (See consent form for details)..

14. Compensation for Research-Related Injury

This section is not required when research involves no more than Minimal Risk to subjects. **N/A**

a. *Describe the available compensation in the event of research related injury.*

N/A

15. Resources Available

N/A

a. *Availability of medical or psychological resources that subjects might need as a result of an anticipated consequences of the human research.*

N/A

b. *Process to ensure that all persons assisting with the research are adequately informed about the protocol, the research procedures, and their duties and functions.*

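### Skin reaction to the dressing is the dressing-related risk the protocol names, yet it has no data field, no inspection scheduled after removal, and no planned summary by arm

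*Combined protocol and SAP*

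**What the plan says.** - **Risk named.** Section 10.a foresees nothing beyond standard care except this: "Topical or allergic reactions to the dressing materials would be managed by removal of the dressing and topical treatments". Sections 6.c and 9.a name the same risk.
- **Detection.** Section 6.c states: "Visual evaluation of the site of insertion of the epidural catheter will be inspected during the study period". It promises that a reaction found in this way will be recognised and dealt with. It gives no time point, observer, criterion or record.
- **Final record.** Section 7.c.i places it an hour after the birth and says: "immediately before catheter removal, time, duration of catheter presence, centimeters from skin to catheter tip and dressing integrity will be recorded". The records made during labour cover the block, top-ups, infusion rate and catheter replacement. Neither set has a skin item.
- **End of participation.** Section 6.d: "The patients will be participating in the study for as long as the epidural catheter remains in place for clinical indications".
- **Outcomes.** The primary outcome is migration in centimetres. The five secondary outcomes concern sensory level, asymmetry, replacement, dose and top-ups.
- **Safety data.** Section 8.c is headed as the collection of safety information. Its text is "Data will be de-identified right after collection and be kept as paper record in the PI office", and it names no variable.
- **Consequence of a reaction.** Section 9.a: "Patients will be withdrawn from the study if she develops an allergic or topical reaction to dressing". The same sentence covers dressings replaced for soiling or bleeding. Section 9.c gives all of these, and consent withdrawals, one label (lost to follow-up), to be reported in the results.

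**The concern.** Because the randomised comparison is between adhesive materials, a skin reaction is the most direct possible drawback of whichever dressing holds the catheter best. The hypothesis is that one combination is superior, and it is framed on migration, block quality and failure, and replacement. The plan promises that reactions will be identified, but its data section gives no place to write them down, and nobody is scheduled to look once the dressing is off.

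Two things are at stake. First, a low count of reported reactions could be read as evidence of skin safety when it may only reflect the lack of a field. Second, the reactions that are recognised disappear into a mixed category, so a reader of the results could not tell how many there were or in which arm. A skin finding not recorded at removal cannot be recovered at analysis.

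**Working it through.** **1. The plan's own figure.** The only design figure is 35 per group, for a 0.5 cm difference at 90% power and alpha 0.05. No standard deviation is stated, so it cannot be reproduced. Solving backwards for a two-sided comparison of two means:

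SD = 0.5 × √(35/2) / (1.960 + 1.282) = 0.645 cm.

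That figure concerns migration and does not bear on this point. What matters here is 35 per arm, 3 × 35 = 105 in all.

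**2. Following a reaction through the plan.**

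| When first visible | Provision that applies | What the plan records |
|---|---|---|
| During labour, with the dressing on | Inspection under 6.c; withdrawal under 9.a | No field in 7.c.i; pooled under the 9.c label, with no cause or arm specified |
| Dressing lifted, catheter still in | Still within participation (6.d), so 6.c and 9.a apply | As above |
| After the catheter is out | Participation over; no observation scheduled | Nothing, unless it qualifies under the general event route in 8.a |

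The documents do not say when the dressing is lifted relative to the final reading. Scoring dressing integrity at that visit suggests it is on at that moment, but this is an inference. The order decides whether the second or third row applies. In neither row is there a field or outcome for the finding.

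**3. Size of the loss.** It would be (true rate) × (share missed) in each arm, and the documents give neither term. As an illustration only, assume a true rate of 10% in every arm and detection of 90% in one arm against 30% in another:

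- 35 × 0.10 × 0.90 = 3.15 observed reactions
- 35 × 0.10 × 0.30 = 1.05 observed reactions

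Equal true rates would then look like roughly a threefold difference. The inputs are assumptions, so this shows a mechanism and is not an estimate.

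**4. What complete recording could support at this sample size.**

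- One-sided 95% exact upper limit after no reactions in one arm: 1 − 0.05^(1/35) = 8.2%. Over all arms: 1 − 0.05^(1/105) = 2.8%.
- Chance of seeing no reaction in an arm, (1 − p)^35: 49% at p = 2%, 17% at 5%, 2.5% at 10%.
- Power of a pairwise Fisher exact test at 35 per arm (assumed rates): 2% v 10%, 0.07; 5% v 20%, 0.33; 5% v 30%, 0.74.

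These figures reflect sample size and would be the same after the fix. They do not measure the defect; they show that the result should be a descriptive table.

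**The case against.** The plan is not silent. Section 6.c provides for inspection, 9.a makes a reaction a reason for withdrawal, 9.c requires withdrawn cases to be reported, and 8.a has ongoing event review with a five-business-day reporting limit. A reader might infer that reactions are certainly missed and that the safety review has nothing to look at. The documents do not support that: some detection and reporting is planned, and 8.a refers to a monitoring plan whose detail is not shown. What stands against the plan is narrower. The inspection has no schedule or record and names only the insertion site, the withdrawal route hides the cause, and nothing says a mild local reaction counts as reportable.

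A reader might also infer that detection is probably worse in the arms with more material. The hypothesis calls Tegaderm transparent, but no section describes how well skin can be seen under the other components, or how much adhesive each arm carries. Unequal detection is possible and no more than that.

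Finally, known adhesive allergy is excluded, expected exposure is 6 to 12 hours, all three dressings are current practice, and a by-arm table at this size would rarely separate the arms. All of that is fair. It limits the importance of the point and rules out calling for a powered comparison, but it does not explain why the one named risk of the materials under test has no field.

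**Conclusion.** The gap is real and modest. It is established from the text that no skin item is recorded, no observation is scheduled after catheter removal, no reaction outcome or by-arm summary is planned, and reaction withdrawals are pooled with others. It follows that reactions seen only when the dressing is lifted may go unrecorded, possibly unequally by arm, and that recognised reactions are not reported as such.

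How many would be lost cannot be derived from the documents; any number depends on an assumed reaction rate and an assumed share hidden until removal. The migration analysis is not biased by the missing field itself. A stronger reading, that the trial would end up recommending a dressing that harms skin, needs reaction rates and visibility that the documents do not give. The change is worth making because it is cheap and the information cannot be collected afterwards.

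**What to change.** 1. **7.c.i:** add one yes/no item for skin reaction over the whole dressed area, with type (redness, blister, skin tear, other), completed at the same visit once both dressing and catheter are off.
2. **6.d:** extend participation to the end of that inspection.
3. **Outcomes:** add skin reaction to the dressing, by randomised arm, as a descriptive safety outcome. Count reactions that led to withdrawal under 9.a, and report them separately from consent withdrawals and soiled or bleeding dressings.
4. **8.c:** name this item as safety information collected, so that it reaches the review in 8.a.
5. **9.a and 9.c:** reconcile these with the new item. With participation extended and the present wording kept, redness first seen after the final reading could class a woman with a complete migration measurement as lost to follow-up. State that such a finding does not remove her primary outcome.

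The cost is one form line, under a minute per patient, and consistent edits to these sections. No extra visit, staff or procedure is needed, because the dressing comes off anyway. The table should give counts per arm with exact confidence limits and should not be presented as a test of difference.
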